Insomnia and maternal and infant outcomes. Insomnia during pregnancy has consequences for maternal and child health. For example, insomnia in pregnancy has been associated with numerous pregnancy complications including: preeclampsia, preterm birth and growth retardation (5). Experiencing poor sleep quality in pregnancy has been shown to predict poor newborn sleep (6) and symptoms of maternal postpartum depression (PPD) (7, 8). In fact, experiencing a sleep trajectory characterized by consistent poor sleep quality in the perinatal period or development of poor sleep quality in the third trimester of pregnancy has been associated with ten to twenty-fold increases in the risk of experiencing symptoms indicative of PPD, even after controlling for robust predictors of PPD such as depression in pregnancy, and socioeconomic status (8). PPD is itself associated with numerous negative child outcomes (9).

Treatment of insomnia in pregnancy. Treating antenatal insomnia with pharmacotherapy effectively improves sleep quality and confers a protective benefit against the onset of PPD (10); however, recent best practice guidelines advise against the use of sleep medications in pregnancy due to potential teratogenicity (11). Additionally, data suggests that the majority of pregnant women are reluctant to take prescribed medications due to their perception of risk (12, 13). Results from a recent study conducted in our lab, assessing patient perceptions, found that when presented with descriptions of pharmacotherapy versus cognitive behavioural therapy for insomnia (CBT-I), pregnant women rated CBT-I as significantly more credible and indicated that it was a preferable treatment for insomnia experienced in pregnancy when compared to pharmacotherapy (14).

Cognitive Behavioural Therapy for Insomnia (CBT-I). CBT-I is an evidence-based psychotherapeutic intervention that combines cognitive and behavioural principles to provide psychoeducation about thoughts that contribute to the maintenance of sleep problems, and instruction in behavioural techniques to help participants decrease sleep onset latency and promote effective sleep maintenance. A large body of research has demonstrated that CBT-I is an effective treatment for insomnia, with short-term efficacy equivalent to medication, and long-term results suggesting that it outperforms medication. For example, in a review of

randomized controlled trials that assessed the comparative effectiveness of CBT-I and pharmacological interventions for insomnia, it was found that CBT-I was more effective than benzodiazepine and non-benzodiazepine drugs in the long term (15). Additionally, meta-analysis suggests that effect sizes of CBT-I range from medium to large both at post-treatment and follow-up assessments (15), prompting researchers to recommend primary care providers to consider CBT-I as the first treatment option for insomnia (16).

Online CBT-I. Despite an encouraging body of evidence supporting the use of CBT-I for treatment of insomnia and treatment with CBT-I is not easily accessible to all pregnant women. There are also a lack of well-trained CBT-I therapists and far fewer than would be needed to provide services to the vast number of North American women suffering from insomnia in pregnancy. To address this issue, researchers have turned to online administration of CBT-I (iCBT-I; 17). Two systematic reviews and meta-analyses suggest that iCBT-I is effective at reducing symptoms of both insomnia and depression (18, 19). For the treatment of insomnia, administration of iCBT-I has been shown to be comparable to face-to-face intervention (18, 19).

CBT-I in the Perinatal Period. Pregnant women have traditionally been excluded from intervention research and insomnia treatment is no exception, prompting calls for further development of interventions to treat insomnia in pregnancy and the postpartum (20). To our knowledge, there has only been one open pilot study examining the effectiveness of CBT-I in pregnancy, which was conducted by our lab. The intervention was delivered to thirteen pregnant women with insomnia and results suggest that CBT-I was effective and acceptable in reducing both subjective symptoms of insomnia and improving objective indices of sleep quality; in fact at the end of treatment 12/13 participants said they were no longer experiencing clinically significant symptoms of insomnia (21). Additionally, the intervention was acceptable to participants with 100% of women who began treatment successfully completing the 5-session protocol.

The majority of women entered the study reporting elevated depressive symptoms and experienced a significant decline in depressive symptoms in the follow-up period, a finding that has been observed in other populations (22, 23). These results are encouraging, as recent trajectory analyses from our group show that without intervention, disturbed sleep and depressive symptoms are relatively stable or increasing in the perinatal period (24, 25). Further, results from a systematic review and meta-analysis currently being conducted in our lab, which includes over 4,000 subjects, suggests that on average sleep quality declines significantly from early to late pregnancy; in contrast, group treatment with 5-sessions of CBT-I significantly improved sleep quality, even as pregnancy progressed.

Objectives

The primary aim of the current project is to evaluate the impact of a 6-week in-person CBT-I versus iCBT-I versus a waitlist (WL) in reducing symptoms of insomnia (assessed subjectively by self-report and objectively with actigraphy) experienced in pregnancy. We hypothesize that

participants who receive a 6-week program CBT-I and iCBT-I (versus WL) will report fewer insomnia symptoms and have improved objectively assessed sleep as measured by at one-week (T2) post treatment. Based on previous research findings, we do not expect that there will be a difference between in-person CBT-I and iCBT-I administration.

The secondary aim is to investigate if CBT-I versus WL reduces symptoms of depression at T2 (one week post-treatment). We hypothesize that participants who receive CBT-I and iCBT-I (versus WL) will report fewer depressive symptoms as measured at T2.

METHODS

Trial Design

The proposed study is a randomized controlled trial of the efficacy of CBT-I for the treatment of insomnia experienced during pregnancy compared to WL. Assessments will occur at baseline, between 12-30 weeks of pregnancy (T1), and at one week posttreatment (T2).

Recruitment Strategy

Participants will be recruited through Low Risk Maternity Clinics associated with Primary Care Networks, the Perinatal Mental Health Clinic, and the Foothills Medical Center Women's Mental Health Centre. Participants will also be able to self-refer to the study through several other methods including through posted announcements and pamphlets available in the main areas of family medicine clinics, midwifery clinics, ultrasound clinics, holistic/chiropractic clinics and other areas (community centres, libraries, and children's stores). Participants will also be recruited through advertising on Internet (Healthy Hearts Lab website, Healthy Hearts Lab accounts on Twitter and Facebook). Media releases about the study may also occur in print media, on the radio, and television. In any media releases, active recruitment will not occur; however, the study investigator would give general information about the study, potentially in an interview. A research assistant will explain the study protocols involved in the project to interested participants. If a participant meets the inclusion criteria and agrees to be involved in the study, a baseline assessment will be conducted in the two weeks prior to the start of the intervention.

Inclusion and Exclusion Criteria

Inclusion: English speaking women over the age of 18, between twelve and thirty weeks of gestation, and identify as experiencing insomnia in pregnancy. Insomnia will be diagnosed using the Insomnia Interview Schedule (IIS).

Exclusion: Experiencing symptoms of other sleep disorders (i.e. restless legs syndrome, sleep-disordered breathing); history of untreated, serious psychiatric illness (i.e., bipolar disorder, schizophrenia); currently taking prescribed medications for sleep problems; smoking, drinking alcohol or drug abuse during pregnancy.

Pregnant women interested in study participation will contact the Healthy Hearts Laboratory and will receive additional information about the study protocols involved in the project. If a participant agrees to take part in the study, she will answer a series of questions during a phone-screening questionnaire (Insomnia Interview Schedule) (21). Potential participants who will not meet the inclusion criteria (e.g., reporting mild sleep problems) will be provided by email with a resource list of community services for pregnant women. Pregnant women excluded from the study for smoking, alcohol use, and/or drug use will also be provided with a list of community services, and referred to their primary care physician.

Prospective participants who agree to be involved in the study will meet with a member of the research team, who will explain the study procedures in full detail and obtain written consent. After consent has been obtained, participants will also be administered a diagnostic interview (Structured Clinical Interview for DSM-5; SCID) to assess if any exclusionary criteria are present and collect information about Axis 1 mood disorders (26). Assessments will be conducted by master's students in clinical psychology, under the supervision of a licensed clinical psychologist. Screening for Restless Legs Syndrome (RLS) and sleep-disordered breathing (SDB) will be conducted using the Cambridge-Hopkins questionnaire for Restless Legs Syndrome (CH-RLSq) and STOP questionnaire, respectively; women whose scores are suggestive of a sleep disorder other than insomnia will be referred to their primary care provider for further assessment.

Procedures

Week 1 (T1): Eligible participants will meet with a member of the research team, who will explain the study protocols and obtain written consent. After completing a demographic and health practices questionnaire, women will be asked to read and complete self-report assessments of emotional and physical manifestations of fatigue, emotional health, social support, and sleep quality and quantity. Please see Figure 1 for a research design flowchart.

Once complete, participants will be provided with an actigraphy device and instructed on how to use it. They will be asked to wear the device for a period of 7 days during and send it back in a prepaid, stamped, envelope which will be provided at their study visit.

Participants will be randomly allocated to in-person CBT-I or iCBT-I or WL. Randomization will be determined using an online research randomization tool (27), which is not predictable and eliminates potential experimenter bias (28). Forty-five participants will be enrolled in the pilot RCT, with 15 randomized into each study group. A staff member who is not associated with the study will conduct the randomization and sequence generation and will put each participant assignment into opaque envelopes that contain the results of the randomization. After a baseline assessment is completed a study therapist will open an envelope and inform participants of their assignment.

Participants randomized to in-person or online treatment will be invited to participate in 6 sessions of CBT-I. Participants randomized to the waitlist group, will receive a pamphlet with information about community resources for pregnant women.

Week 2- Week 7: If randomized to the in-person treatment group, participants will be invited to attend 6 in-person sessions of cognitive-behavioural therapy for insomnia, which will take place at the University of Calgary in a newly renovated research space (*see Appendix A for the structure of each session*). Additionally, they will receive a manual which will include weekly readings relevant to the material being taught in the sessions and an informational pamphlet with helpful community resources for pregnant women. During this intervention, they will become familiarized with self-management approach for insomnia, sleep basics and sleep restriction, stimulus control, problem solving to cope with sleep disturbances and relapse prevention.

Participants randomized to online cognitive behavioural treatment (iCBT-I) will complete a series of 6 modules, where the main learning components are included in video and audio materials. To log onto the CBT-I intervention website, participants will be given login information through an anonymized email address, which will be used only for the duration of the study. Like the in-person intervention, the iCBT-I intervention includes instruction and homework on sleep hygiene and relaxation strategies. Participants will be contacted regularly by a member of the study team to ensure that there are no issues with accessing online readings and audio/visual materials (29).

Participants in the waitlist group will receive regular obstetric care provided according to the needs and current regime of the patient. The amount of contact with health care professionals outside of the study will be reported, as well as any treatment for insomnia (e.g., medication use) that the control participant engages in.

Week 8 (T2): After 8 weeks, all the participants will be invited to complete the same set of questionnaires from the baseline assessment. Additionally, they will be provided with an actiwatch and asked to wear it for seven days during weekdays. WL participants will be offered the opportunity to access the iCBT-I treatment.

3-Months Postpartum (T3): At 3-months postpartum, all participants will be invited to a web-link with the same set of questionnaires from the previous points of assessment, as well as one additional questionnaire assessing infant sleep quality. The web-linked questionnaires are expected to take approximately 30 minutes to complete.

Equipment

Participants will be provided with an actigraphy device (Actiwatch II, Phillips, USA) and asked to wear it for 7 consecutive days at each assessment point.

Outcome Measures

Complete descriptions of outcome measures are provided in Table 1.

Primary Outcome Measures

Insomnia Interview Schedule (IIS), Insomnia diagnosis will be confirmed using the IIS, which produces reliable and valid insomnia diagnoses, and provides information about developmental course and impact (21).

Insomnia Severity Index (ISI) (21, 30, 31). The ISI is a 7-item questionnaire designed to identify cases of insomnia and evaluate treatment outcomes. The ISI assesses severity of sleep onset, sleep maintenance and early wakening problems, sleep dissatisfaction and perceived distress caused by sleep problems and it was found to be a clinically useful tool in assessing changes in insomnia symptoms in insomnia treatment research (31).

Pittsburgh Sleep Quality Index (PSQI). The PSQI instrument is used in assessing one's sleep quality during the previous month. It consists of 19 self-rated items and 5 questions rated by the roommate or bed partner. There are seven components of the PSQI and these are subjective sleep quality, sleep latency, sleep duration, habitual sleep efficiency, sleep disturbances, use of sleeping medications and daytime dysfunction. A score higher than 5 suggests poor sleep quality (32).

For assessing sleep quantity and quality, actigraphy (Actiwatch II, Phillips, USA) and sleep daily logs will be used in this study. Actigraphy monitoring provides objective information on circadian rhythm amplitude, acrophase, and mesor as well as indices of sleep efficiency, sleep latency, total sleep time, and number and frequency of awakenings (33). Participants will be asked to wear the actigraph for a period of 7 days at each assessment point.

Secondary Outcome Measures

Edinburgh Postpartum Depression Scale (EPDS) (34). Symptoms of depression in pregnancy and the postpartum will be assessed by the EPDS. The EPDS consists of 10 items and is a reliable and valid tool for identifying symptoms of depression experienced in pregnancy and the postpartum (35).

Additional Measures and Questionnaires

Additional questionnaires include the Multidimensional Fatigue Symptom Inventory-Short Form (MFSI-SF) (36), Dysfunctional Beliefs and Attitudes about Sleep Questionnaire (DBAS-16) (37), Sleep Self-Efficacy Scale (SES) (38), Sleep Hygiene Index (39), Pre-Sleep Arousal Scale (40), Glasgow Sleep Effort Scale (41), Sleep-Related Behaviors Questionnaire (SBRQ) (42), Epworth Sleepiness Scale (ESS) (43), Edinburgh Postnatal

Depression Scale (EPDS) (88), Generalized Anxiety Disorder (GAD-7) (44), Couple Satisfaction Index (CSI-16) (45), the Big Five Inventory (BFI-44) (46), the Extended Brief Infant Sleep Questionnaire (BISQ) (47), the Pregnancy-Specific Anxiety Measure (48), the PROMIS Adult Version 1.0 Pain Interference Short Form 8a (49), and the PROMIS Adult Version 1.0 Pain Intensity Short Form 3a (49).

Data will also be collected regarding demographic and psychosocial variables known to impact sleep. Demographic information collected will include age, family socioeconomic status, and number of children at home. Health practices assessed include smoking, alcohol consumption, and level of habitual exercise. Assessment of previous mental health problems, sleep disorders and psychotropic medication use will be assessed via interview.

ANALYSIS PLAN

Sample Size Power Calculation

The primary response variable, change in symptoms on the Insomnia Severity Index (ISI) between baseline (T2) and post treatment follow-up (T2), will be analyzed with using Repeated Measures Analysis of Variance (ANOVA) with a linear distribution specified at a significance level of $\alpha = 0.05$. Using data from our pilot study, and insomnia symptoms on the ISI, we found that pre-post treatment yielded a $d = 3.07$. Prior studies of CBT-I for patients with insomnia have found large between-group effect sizes in a range from $d = 1.1$ to $d = 1.6$, even in patients with comorbid mental illness; however, we completed our power calculations using a more conservative effect size estimate, which showed that 18 patients are required to have a 95% chance of detecting a between-group effect size of $d = 0.8$ at a significance level of $\alpha = 0.05$ on the ISI. Although we had no attrition from our pilot study, we added a potential attrition rate of 20%, resulting in 14 participants to detect group differences in our pilot RCT.

Based on previous research, we do not expect to see differences in iCBT-I versus in person CBT-I; however, we expect that both conditions will outperform the WL group. Although we had no attrition from our pilot study, we calculated a potential attrition rate of 20% based on previous research in this area, resulting in 45 participants in our pilot RCT. Across 3 arms, this will allow 14 participants in each group and will provide a power of more than 90% to detect a difference of 8 points on the ISI, which is indicative of a clinically significant change (30).

Primary Aims

Hypothesis 1) Participants who receive in-person and online CBT-I (versus WL) will report fewer insomnia symptoms as measured by Insomnia Severity Index (ISI) at the post treatment assessment point (T2).

Primary aims will be assessed using Generalized Estimated Equations (GEE) and an intent-to-treat (ITT) basis, including data for each participant who was randomized, regardless of their

adherence to the intervention or whether they withdraw from the study. Analyses including only patients fulfilling the treatment will also be conducted.

Secondary Aims

Hypothesis 2.1) Participants who receive in-person and online CBT-I (versus WL) will experience fewer symptoms of depression as assessed by the Edinburgh Postpartum Depression Scale (EPDS) and will be less likely to be diagnosed with depression as assessed using Structured Clinical Interview for the DSM-IV (SCID) at T2.

Hypothesis 2.2) Participants who receive online and in-person CBT-I (versus WL) will be less likely to be diagnosed with insomnia, as measured by the Insomnia Interview Schedule (21), at T2.

Hypothesis 2.3) Participants who receive in-person and online CBT-I (versus WL) will experience better objective sleep as assessed by actigraphy (higher sleep efficiency and lower sleep onset latency) at T2.

Secondary aims including changes in actigraphy parameters, diagnosis of insomnia, symptoms of and diagnoses of depression will be examined. Changes in binary outcomes will be tested using Generalized Estimated Equations (GEE) with a binary outcome specified.

RESEARCH MANAGEMENT

[name], as the Primary Investigator will be responsible for the overall management of the project. She received extensive training in cognitive behavioral interventions and will be responsible for training clinical psychology master's students in the delivery of in-person cognitive behavioural therapy for insomnia adapted for pregnant women. [name] is an experienced clinician and will provide clinical support regarding the establishment of therapy protocols and ongoing consultation regarding fidelity to the CBT treatment protocol. [name] will be responsible for supervising master's students in administering diagnostic interviews for Axis I mood disorders. [name] will be responsible for supervising the research assistant at the University of Manitoba who will be coordinating the online portion of the intervention.

RESEARCH ENVIRONMENT

All assessments and in-person CBT-I sessions will take place at the University of Calgary in a newly renovated research space designed specifically for conducting and evaluating evidence-based interventions which is located in suite 292 of the Education Classroom Building.

REFERENCES

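### The primary ISI analysis names no baseline covariate although women enter over an 18-week gestational span; prespecify baseline ISI and gestational age at T1, for a modest gain in precision and protection against chance imbalance

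*Combined protocol and SAP*

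**What the plan says.** The background section on CBT-I in the perinatal period makes two statements about the untreated course. One, from the group's trajectory analyses, is that "without intervention, disturbed sleep and depressive symptoms are relatively stable or increasing in the perinatal period". The other, from a review in progress, is that "on average sleep quality declines significantly from early to late pregnancy". An earlier background paragraph separates women who sleep badly throughout the perinatal period from those whose sleep deteriorates only in the third trimester.

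Inclusion and Exclusion Criteria admit women "between twelve and thirty weeks of gestation". Procedures describe allocation by an online tool, "with 15 randomized into each study group", and name no stratification factor. Figure 1 is not available, so a note on stratification there cannot be ruled out. T2 follows the same schedule in every arm: "After 8 weeks, all the participants will be invited to complete the same set of questionnaires from the baseline assessment".

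The sample-size section defines the primary response as change in ISI from baseline to T2 and names repeated-measures ANOVA. The Primary Aims section says instead: "Primary aims will be assessed using Generalized Estimated Equations (GEE) and an intent-to-treat (ITT) basis". Neither place lists a covariate, and the model terms are not written out. The section on additional measures promises data on variables known to affect sleep. Gestational age is not in its list, and none of the variables is assigned to the model.

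**The concern.** Gestational age is known for every woman, because it decides eligibility. The protocol itself presents gestation as related to sleep. With T2 at about 8 weeks, a woman who enters at week 12 is followed to about week 20, and one who enters at week 30 to about week 38. If untreated ISI change differs between those two stretches of pregnancy, arms that differ by chance in entry gestation will also differ in expected change. In addition, the variation that gestation explains stays in the error term.

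With 15 women per arm, an imbalance of a few weeks is plausible. If nothing is prespecified, adjusting after an imbalance has been seen becomes a data-driven choice.

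**Working it through.** The plan gives no figure for gestation, so there is none to reproduce. Taken from the documents: the 12–30 week window, 15 per arm, a T1–T2 interval of about 8 weeks and the 8-point ISI target. Assumed: the spread of entry gestation, the slope of ISI change on entry gestation, and a residual SD of change of 5.5 points.

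**1. Imbalance in entry gestation**

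- Even entry over 18 weeks: SD = 18/√12 = 5.20 weeks.
- SE of the difference between two arms of 15 = 5.20 × √(2/15) = 1.90 weeks; 95% range = ±1.96 × 1.90 = ±3.7 weeks.
- One comparison: P(difference > 3 weeks) = 2 × [1 − Φ(3/1.90)] = 11%.
- Either CBT-I arm against waitlist (the two comparisons share the waitlist arm, so this is simulated, 200,000 draws): 20%.

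| Entry SD (weeks) | SE, 15 v 15 (weeks) | P(either arm > 3 weeks from waitlist) |
|---|---|---|
| 5.2 | 1.90 | 20% |
| 4 | 1.46 | 7% |
| 3 | 1.10 | 1% |

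If the CBT-I arms are pooled (30 v 15), the SE under even entry is 5.20 × √(1/15 + 1/30) = 1.64 weeks and P(> 3 weeks) is 7%.

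**2. Shift in the ISI contrast**

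Shift = slope × imbalance. At the 95% limit of 3.7 weeks:

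- slope 0.1 points per week: 0.1 × 3.7 = 0.4 points
- slope 0.4 points per week: 0.4 × 3.7 = 1.5 points

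The upper slope is generous. It means that untreated change differs by 0.4 × 18 = 7.2 points between the ends of the window, close to the 8-point target.

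**3. Effect of adjustment on the standard error**

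- Correlation of entry gestation with change: r = 5.20b/√[(5.20b)² + 5.5²], which is 0.09 at b = 0.1 and 0.35 at b = 0.4.
- Residual variation removed: √(1 − r²) − 1 = −0.4% to −6.5%.
- Adjustment also has a price, the lost degree of freedom and the chance correlation of gestation with arm. With 45 women and 3 arm means, this inflates the variance by about 1 + 1/(45 − 3 − 2) = 1.025, or about 1.2% on the SE.

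Simulation with both parts included (45 women, 3 arms, 10,000 trials per slope):

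| Slope (ISI points per week) | Mean change in SE |
|---|---|
| 0.1 | +0.8% |
| 0.2 | −0.6% |
| 0.3 | −2.6% |
| 0.4 | −5.4% |

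Break-even is near 0.17 points per week.

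**4. Validity of the unadjusted test**

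In simulated 15 v 15 comparisons, overall type I error was 4.8% to 5.1%, with mean error near zero. Among trials with an imbalance above 3 weeks it was 6.2% (r = 0.2), 8.2% (r = 0.3) and 13.5% (r = 0.5, beyond the slope range above).

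**5. Which term helps**

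Suppose the GEE is arm × time; the plan does not say. Gestation at entry is constant within a woman, so with complete data a main effect cannot alter her change. In a simulated data set of 45 women the two arm × time estimates were −4.71 and −5.70 with no gestational term, and exactly the same with a main effect. With gestational age × time they became −4.48 and −5.44.

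**The case against.** A reader might infer that the missing covariate biases the treatment effect. It does not. Randomisation makes the unadjusted contrast unbiased on average, and its standard error already allows for chance imbalance.

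A reader might also infer that the protocol shows untreated ISI change to depend on entry gestation. It does not show that either. The review statement concerns average sleep quality, not the ISI, and is not said to be restricted to women with insomnia. The companion statement is that disturbance is stable or increasing. The primary response is change over the same interval in all arms with a concurrent waitlist, so a steady decline common to all women cancels. Entry gestation matters only if the course is uneven. The contrast between women who sleep badly throughout and those who deteriorate in the third trimester points that way, but no slope is given.

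These objections stand and limit the point. They do not remove it, for two reasons. First, correct error rates over all randomisations are compatible with a misleading result in one imbalanced trial. Second, not every outcome is protected by differencing. Insomnia on the interview schedule is an entry criterion, so its diagnosis at T2 (Hypothesis 2.2) is in effect compared at T2 alone, and any effect of gestation on level enters directly. Hypothesis 1 is also worded in terms of symptoms at T2.

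**Conclusion.** The point holds as one of precision and of protection against chance imbalance, not of bias. The plan treats gestation as related to sleep, recruits over 18 weeks of it, and prespecifies no baseline covariate. Under even entry, imbalances up to about 3.7 weeks between two arms are within the ordinary range; narrower entry makes them clearly smaller. The effect on the ISI contrast is probably modest: 0.4 to 1.5 points at the limit of that range, under slopes that are assumptions, against a target of 8. The effect on the standard error runs from slightly worse to about 5% better. The documents support no firmer figure. The change is still worth making, because it uses information already needed for eligibility and settles the choice of adjustment before data are seen.

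**What to change.** In the Primary Aims section, prespecify one of the following:

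- a model for ISI at T2 with arm, baseline ISI and gestational age at T1 (continuous, in weeks); or
- if the repeated-measures GEE is kept, arm × time plus gestational age at T1 × time. A gestational main effect alone is not enough.

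Use the same form for the other continuous T2 outcomes. State that gestational age at T1 is recorded as a baseline variable, and report it by arm, so that outcomes in effect compared at T2 alone, such as insomnia diagnosis, can be read against it.

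Stratifying the envelopes by gestation is not proposed. It balances the arms only if each list is also blocked, and it complicates the fixed 15 per arm.

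The cost is a sentence or two in the plan, one degree of freedom for gestation, and a slight loss of precision if gestation proves nearly unrelated to ISI change. No new data are needed. The T2 model uses only women with a T2 score, so if it is chosen the plan should say how that fits its commitment to include everyone randomised.
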